5.3 Method

Patients that meet the inclusion and exclusion criteria will be randomized to either

A: Intervention

Needle-tenotomy

Off-loading Treatment

B: Conservative Treatment

Offloading treatment

Both groups will also be offered offloading treatment in the form of therapeutic sandals with individualized insoles.

5.3.1 Needle Tenotomy Procedure

Patient is placed in seated posture with feet elevated. The toe(s) with hammer, mallet or claw toe deformity is anesthetized by a digital toe block with 1-5 ml of 1% lidocaine administered for each toe. The toe digital block is administered through a plantar approach, at the web level of the deformed toe(s), with a 0,6 mm diameter and 30mm long needle.

After anesthetizing the toe(s) the plantar aspect of the toe at web level is disinfected with an alcohol based disinfectant twice.

Both the long and short flexors are then severed with a 1.2mm diameter and 40mm long needle through a plantar approach, immediately proximal to the web level of the toe.

After the procedure a dry gauze bandage is applied and the patients treated foot/feet is/are elevated for 20 minutes to achieve haemostasis, and the bandage is checked for bleeding before discharge.

5.3.2 Offloading Treatment

Offloading Treatment: The patient's ulcer and deformity are offloaded by treatment with one or a combination of the following treatments:

- Therapeutic sandals with rocker-bottom and individual insoles
- Silicone device
- Handmade shoes with rocker-bottom and individual insoles
- Air-cast Walker
- Felt pad
- Capsule
- Own shoes and individual insoles

5.4 Visit-plan

Patients in both the intervention and conservative groups will be expected to adhere to a specified visit-plan

Visit-plan Study IV	Inclusion	Day 0	Day 7	Day 14	End ¹	Follow-
						up ²
	0.1	a a b b	a	a a a i	2.0	2 0
Duration	3 hours	30 min	30 min	30 min	30	30 min
					min	
In/exclusion criteria	+					
Baseline blood samples and physical	+					
exam						
Patient history	+					
Foot Examination	+	+	+	+	+	+
Changes in Medicine/ new ailments			+	+	+	+
Toe systolic blood pressure (TSB)	+					
Ankle/brachial pressure index (ABPI)						
Neurological assessment	+					
Randomization	+					
Tenotomy/silicone spacer application ³		+				
Standard Care & offloading	+	+	+	+	+	+
Footwear assessment		$+^{4}$	+	+	+	+

1: This visit only happens if patient incurs on of the named endpoints

2: Follow-up visits are performed at 3, 6 and 12 months

- 3: Depending on allocated treatment
- 4: All Patients receive therapeutic sandals with individualized insole

5.5 Detailed description of visits

The following section describes all visits in the study. All visits will be conducted by trained scientific staff, under responsibility of site investigator, and according to the delegation log. Procedures included in the visits will be conducted according to standard operating protocol (SOP) and manual of operations (MOP). It is the responsibility of principal investigator to train scientific staff in SOP and MOP. And to ensure that relevant SOP and MOP are available for the study personnel before procedures are performed.

5.5.1 Inclusion

Inclusion visit can only take place when written consent form is signed by patient, and filed in patient log.

The following procedures will be performed:

- In/exclusion criteria (see section 5.2)
- Baseline blood samples including:
 - o Hemoglobin A₁C
 - o Creatinine
 - o Estimated glomerular filtration rate
 - o Hemoglobin
 - o Albumin
 - o International normalized ratio
 - Low-density lipoproteins
 - o Leucocytes
 - o C-reactive protein
 - All blood samples are analyzed immediately, and nothing is preserved in biobank.
 The total amount of blood is evaluated to be less than 50ml pr. patient.
- Baseline physical examination including measurements of:
 - o Blood pressure
 - o Heart rate
 - Oxygen Saturation
 - o Heart and pulmonary auscultation
 - o Electro Cardiogram

- o Height
- o Weight
- Patient history including information on:
 - o Gender
 - male or female
 - o Diabetes type
 - 1 or 2
 - Duration of diabetes
 - measured in years with no decimal
 - o Duration of foot ulcer
 - measured in days
 - Competing diseases/comorbidity (ASA group is also registered)
 - By diagnosis and year of debut
 - o Current medicine
 - quantity and type
 - \circ Smoking
 - quantity and nature, present or past
 - Alcohol intake
 - quantity
 - Height, weight and BMI
 - In m(two decimals), kg(one decimal) and kg/m²(one decimal)
 - o Prior surgery on feet
 - Type and year
 - Prior ulcers of feet/legs
 - Location and year
 - Prior amputations
 - Location, type and year
 - o Prior/current history of Charcot's ailment
 - Debut year
 - Activity
 - Retinopathy
 - Simplex, proliferative and/or laser treated

- o Urinary albumin excretion rate
 - Normal, micro-, macro- or prior albuminuria
- Peripheral neuropathy
 - Yes/no
 - Pain associated with?
- Prior offloading therapy
 - Type
- o Relationship status
 - Married yes/no and/or living with partner yes/no
- Foot examination
 - Inspection of pressure point, and deformities
 - o Pulses
 - Deformities
- TSBP and ABPI
 - o TSBP and ABPI are performed by educated staff and results evaluated
 - Patients with TSB under 30 mmHg are referred to department of vascular surgery where deemed necessary
- Neurological assessment
 - o Biothesiometry tests are performed by educated staff
 - Monofilament testing is performed by educated staff
 - Neuropathy symptoms are examined and registered
- Randomization
 - o Randomization is performed in RedCAP
- Impending ulcer evaluation
 - Anatomical placement

5.5.2 Visit Day 0

- Foot examination
 - Inspection of pressure point, and deformities
 - o Pulses
 - o Deformities
 - o New Ulcers

- Standard care & offloading
 - See section 5.3.2
- Tenotomy/conservative treatment application
 - The allocated treatment is performed
 - For details on tenotomy see section 5.3.1
 - For details on conservative treatment see section 5.3.2
- Impending ulcer evaluation
 - Anatomical placement
- Ulcer evaluation (if ulcer incurred)
 - Assessment of ulcer surroundings
 - Assessment of infection
 - Assessment of healing
- Measurement of longest length, width and depth in mm
- Measurement of area in mm³(length*width*depth)
 - Assessment of incision site (where applicable)
 - o Measurement of length, width and depth of ulcer(s) after debridement
- Categorizing by Texas Grading System
- Footwear assessment
 - Footwear and/or current offloading is evaluated
 - All patients in conservative and treatment group will be offered therapeutic sandals with customized insole at this visit
- Changes in medicine/new ailments
 - o Changes to the patient's medicine, and/or new diagnosis are registered

5.5.3 Visit Day 7, 14

The following is a specification of the above mentioned visits. If at any visit, before week 10, the impending ulcer has been deemed as progressed to active ulcer, patient is planned for end visit. If Patient incurs ulcer between visit day 14 and 3 month visit, patient contacts study personal to arrange end visit as soon as possible.

• Foot examination

- Inspection of pressure point, and deformities
- o Pulses
- o Deformities
- New Ulcers (not associated to registered impending ulcers)
- Changes in medicine/new ailments
 - o Changes to the patient's medicine, and/or new diagnosis are registered
- Standard care & offloading
 - See section 5.3.2
- Impending ulcer
 - Has impending ulcer progressed to active ulcer
- Ulcer evaluation (if relevant)
 - o Assessment of ulcer surroundings
 - o Assessment of infection
 - Assessment of healing
 - o Ulcer photo
 - o Measurement of longest length, width and depth in mm
 - Measurement of area in mm³(length*width*depth)
 - Assessment of incision site (where applicable)
 - o Measurement of length, width and depth of ulcer(s) after debridement
 - o Categorizing by Texas Grading System
- Footwear assessment
 - o Footwear and/or current offloading is evaluated
- Complications
 - Complications associated with tenotomy is registered (if relevant)
 - SAE is registered (if relevant)

5.5.4 End

End visit is only performed if patients impending ulcer(s) has progressed to active ulcer(s), or impending ulcer has not progressed to active ulcer at 12 month visit.

- Foot examination
 - Inspection of pressure point, and deformities
 - o Pulses

- \circ Deformities
- \circ New Ulcers (not associated with registered impending ulcers at visit day 0
- Changes in medicine/new ailments
 - o Changes to the patient's medicine, and/or new diagnosis are registered
- Standard care & offloading
 - See section 5.3.2
- Impending ulcer
 - Has impending ulcer progressed to active ulcer
- Ulcer evaluation (if relevant)
 - Assessment of ulcer surroundings
 - Assessment of infection
 - o Assessment of healing
 - o Ulcer photo
 - o Measurement of longest length, width and depth in mm
 - Measurement of area in mm³(length*width*depth)
 - Assessment of incision site (where applicable)
 - o Measurement of length, width and depth of ulcer(s) after debridement
 - Categorizing by Texas Grading System
 - Footwear assessment
 - Footwear and/or current offloading is evaluated
 - Complications
 - Complications associated with tenotomy is registered (if relevant)
 - SAE is registered (if relevant)

5.5.5 Follow up

The following is a specification follow up visits. Performed at 3, 6 and 12 months post day 0 visit

- Foot examination
 - Inspection of pressure point, and deformities
 - o Pulses
 - o Deformities
 - o New Ulcers
- Changes in medicine/new ailments

- o Changes to the patient's medicine, and/or new diagnosis are registered
- Standard care & offloading
 - See section 5.3.2
- Impending ulcer
 - Has impending ulcer progressed to active ulcer
- Ulcer evaluation (if relevant)
 - Assessment of ulcer surroundings
 - Assessment of infection
 - Assessment of healing
 - Ulcer photo
 - o Measurement of longest length, width and depth in mm
 - Measurement of area in mm³(length*width*depth)
 - Assessment of incision site (where applicable)
 - Measurement of length, width and depth of ulcer(s) after debridement
 - o Categorizing by Texas Grading System
 - Footwear assessment
 - \circ $\;$ Footwear and/or current offloading is evaluated
 - Complications
 - Complications associated with tenotomy is registered (if relevant)
 - o SAE is registered (if relevant

5.6 Randomization

- Will be done in an open source electronic data capturing system (REDCaP), using the REDCaP Randomization module. This is based on an allocation table which will be generated by a statistician at our institute, with no other connection to the study.
- Patients will be block randomized, and stratified by treatment facility. Blocks will be of 5 patients each, stratified by study site.

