5. STUDY I

5.1 Design

A prospective RCT involving patients with diabetes as well as one of the three deformities and an impending ulcer associated with the mentioned deformities. By randomization, patients will be allocated to either conservative treatment or tenotomy performed by needle.

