5.2 Patients

Inclusion criteria

- Patients aged 18 years or above
- Type 1 or 2 diabetes
- Hammer, mallet or claw toe deformity
- Impending ulcer associated with above mentioned deformities
- Able to understand written and oral information
- Ability to follow planned visits and treatment
- Able to provide informed consent in Danish and/or English

Exclusion criteria

- Revascularization procedure in the affected limb planned, or undertaken within the 4 weeks prior to screening
- Hammer, mallet and claw toe that are rigid in both MTP, IP joints
- Ulcer associated with hammer, mallet and claw toe deformities
- Toe pressure < 30mmHg
- Prior major amputations on affected or ipsilateral leg
- Other corrective operation is indicated to treat patients foot deformities as deemed by investigator
- Current treatment with cytotoxic drugs or with systemically administered glucocorticoids
- Treatment of foot ulcers with growth factors, stem cells or equivalent preparations within the 8 weeks prior to screening
- Likely inability to comply with the need for planned visits because of planned activity
- Participation in another interventional clinical foot ulcer-healing trial within the 4 weeks prior to screening
- Prior enrolment in this trial
- Judgement by the investigator that the patient does not have the capacity to understand the study procedures or provide written informed consent

Discontinuation of patients

- Patient discontinues assigned treatment for any reason, while not fulfilling one of the studies accepted endpoints
- Participants who withdraw from treatment will be asked to remain in the trial for follow-up, and data will continue to be collected and analyzed.
- Patient incurs a serious adverse event (SAE), defined as death or sepsis related to the study procedure

- Investigator decides to discontinue patient due to health or compliance reasons
- Patient misses 3 consecutive visits
- Patient misses 5 or more visits during the full treatment period

Patients who discontinue the study early will be invited to have a clinical visit before being discontinued.

Patients that are discontinued will revert to their normal treatment plan, and continue in their respective clinics.

Endpoints

- New ulcer incurred
 - When/if new ulcer is incurred pictures will be send to two external evaluators to be confirmed as new ulcer
- Patient reaches 12 month visit without incurring a new ulcer

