5.8 Statistics

All statistical analysis will be performed using the version of SAS currently used at our institute. All data will be analyzed on the intention to treat basis. All baseline data will be presented using appropriate summarizing statistics. Appropriate comparable statistical analysis will be applied to

- Incidence of new ulcer(s) in treated limb
- Mean time (in days) to healing of incision sites
- Incidence of minor amputations
- Incidence of major amputations

Odds-ratio will be applied to

- The incidence of secondary infection
- Pain in treated limb, associated with tenotomy
- Transfer lesion

Sample-size

The calculation is done with a Type 1 error rate (α) at 5%, and a power (1- β) at 80%. The primary endpoint is number of new ulcers incurred.

In the general diabetic population life time prevalence of diabetic ulcers has been reported at $15-25\%^{24}$, the yearly incidence in the same group is 6%. This study focuses on patients with a deformity reported to have a 1.5 hazard ratio²⁵, and signs of an impending ulcer like callus formation, which has been reported with a relative risk of 11^{26} . The incidence of new diabetic foot ulcers incurred by the study population is set at 10%, according to the above mentioned considerations.

The incidence in the intervention group (μ_A) is set at 6%, so the anticipated reduction in incidence is 4% compared to the incidence in the control group (μ_B) which as above mentioned is set at 10%. However, the numbers for incidence of new diabetic foot ulcers is an uncertain size, especially when looking at the specific group we are looking at, therefore the standard deviation (σ) is set at 10.

The calculator used is a 2 means, 2 sample, 2-sided equality calculator. The formula is

 $nB=(1+1/\kappa) ((\sigma z1-\alpha/2+z1-\beta)/(\mu A-\mu B))2$

nB= Sample size

 κ = The matching ratio

With the above described parameters, the sample size is 98 patients, which due to an expected dropout of 10% will be extended to 110 patients.

6. **Perspective**

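### Section 5.6 fixes and discloses a block size of 5 per site, which cannot give the 1:1 allocation that 5.8 implies and lets some later assignments be deduced from earlier ones

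*Combined protocol and SAP*

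**What the plan says.** Section 5.6 uses the REDCap randomization module with permuted blocks within each site: "Blocks will be of 5 patients each, stratified by study site". The module reads from "an allocation table which will be generated by a statistician at our institute", and that statistician has no other link to the study. Section 5.1 sets two arms: "patients will be allocated to either conservative treatment or tenotomy performed by needle". Neither 5.6 nor any other section gives an allocation ratio or says how the five places of a block divide. In the sample-size part of 5.8, kappa is defined as "The matching ratio" but has no value.

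No blinding of patients or staff is described. The section numbers run from 5.6 to 5.8, so this applies to the text as supplied. Under 5.5, "All visits will be conducted by trained scientific staff, under responsibility of site investigator". The criteria check and the randomization step ("Randomization is performed in RedCAP") belong to the same inclusion visit in 5.5.1. At Day 0 (5.5.2), "The allocated treatment is performed". Some criteria in 5.2 rest on judgement, for example "Other corrective operation is indicated to treat patients foot deformities as deemed by investigator". Section 10 (Recruitment) has the primary investigator screening at all three sites.

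**The concern.** With a known block size and visible treatments, allocations already made at a site narrow down those still to come, however well the list itself is guarded. Staff who give or withhold a needle tenotomy see the allocation. If the next assignment is known while an eligibility judgement is open, enrolment can be steered, and an intention-to-treat analysis cannot undo selection that took place before randomization.

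The comparison is small. At the planned 10% and 6%, 55 patients per arm give 55 × 0.10 = 5.5 and 55 × 0.06 = 3.3 expected patients with an ulcer, so a few steered patients could matter.

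There is also a plain gap in specification. The statistician who builds the table must choose a split that the plan does not give, and no complete block of five can match equal allocation.

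**Working it through.** **1. What ratio does 5.8 imply?** Inputs from 5.8: two-sided alpha 5%, power 80%, difference 10 − 6 = 4, standard deviation 10. Reading the formula with the standard deviation multiplying the sum of the two normal quantiles (1.960 + 0.842 = 2.8016):

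n = (1 + 1/kappa) × (10 × 2.8016 / 4)²

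- kappa = 1: 98.1, which is the plan's 98
- kappa = 1.5: 81.8
- kappa = 2/3: 122.6

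Only kappa = 1 reproduces the stated figure. Equal allocation is therefore implied, though never stated.

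**2. How much can be known with certainty?** An assignment counts as certain if every block sequence compatible with the earlier places in that block gives the same next arm. All sequences of length 5 were enumerated. The observer knows the size, the split and every earlier allocation at the site.

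| Split | Certain at places 1 to 5 | Mean | Of 110 | Best guess correct |
|---|---|---|---|---|
| Independent random 3:2 / 2:3 mix | 0, 0, 0, 0.1, 0.4 | 0.5/5 = 10% | 11 | 62% |
| Every block 3:2 | 0, 0, 0.1, 0.4, 1 | 1.5/5 = 30% | 33 | 72% |

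The 3:2 result agrees with the closed form 3/(2+1) + 2/(3+1) = 1.5 per block. These are long-run averages, not limits. In a single block the maximum is 2 of 5 (mixed) or 3 of 5 (3:2). If 3:2 and 2:3 blocks were balanced in pairs and this were known, the average would be 20%. Fixed 4:1 blocks would give 44%.

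**3. What if the split is not known?** Take a true 3:2 table and an observer who knows only the size and the history.

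- 3:2 and 2:3 both thought possible: certainty needs three of one arm already placed, so (0.1 + 0.4)/5 = 10%.
- 4:1 and 1:4 also thought possible: 0%, because three of one arm no longer rules out a fourth.

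**4. What if some earlier allocations are missed?** Let each be seen independently with probability q, with the split known. The mean certain share is 0.1q³ for the mix and 0.2q² + 0.1q³ for fixed 3:2.

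- q = 0.8: 5.1% and 17.9%
- q = 0.5: 1.3% and 6.3%

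**5. Effect on precision.** If all 22 blocks were 3:2, the arms would be 66 and 44. The variance ratio against 55:55 is (1/66 + 1/44)/(2/55) = 1.042, a rise of 4.2%.

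**6. Alternatives.** Simulated with 37 patients at each of 3 sites. This is an assumption, because the plan gives no numbers per site. SD is that of the overall difference in arm sizes.

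| List within site | Certain | Best guess correct | SD |
|---|---|---|---|
| Mixed blocks of 5, size and split known | 10% | 62% | 5.1 |
| Mixed blocks of 5, size not known | not applicable | about 57.5% | 5.1 |
| Biased coin, 2/3 to the arm that is behind | 0% | about 62% | 3.7 |
| Even blocks of 4, 6, 8 at random | about 2% | about 67% | 2.0 |

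The guesser in the second row simply names the arm that is behind. The same guess achieves the 67% for varying even blocks, so that figure does not depend on the sizes leaking.

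**The case against.** The strongest reply is that the block size alone does not reveal assignments. The observer must also know the split, which the plan does not give. That stands: step 3 shows 10%, or none at all, for a true 3:2 table. Staff could learn the split over several blocks, but 5.6 does not disclose it.

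A reader might infer that up to 30% of assignments are knowable from the protocol. The documents do not support this. The 30% needs a fixed 3:2 split that is known to the observer, and such a split contradicts the equal groups implied by 5.8. Nor is 30% an upper bound, as the 4:1 case shows.

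The opportunity to steer is also narrow. An unconnected statistician makes the table, eligibility is first checked from the record, many exclusions are objective, and consent precedes the inclusion visit. These safeguards lower the risk. They do not stop deduction from past visible treatments, and the judgement-based criteria remain.

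Finally, varying even blocks are not better on every measure. Against mixed blocks of 5 they raise best-guess accuracy from 62% (size known) or about 57.5% (size not known) to about 67%. That is correct, and it is why they are offered below only as an alternative.

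**Conclusion.** The point holds in a limited form. The block of 5 as written cannot deliver the 1:1 allocation that 5.8 implies, and disclosing it makes some later assignments deducible. The relevant size is about 10% certain on average, under an independent 3:2/2:3 mix with the size, the split and the full site history known. It would be 30% under uniform 3:2 blocks known to be so, and less wherever the split or part of the history is unknown.

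This is a vulnerability, not evidence of bias: staff would have to track allocations and act on them before eligibility is settled. A reader might also infer a material loss of balance or precision. That does not follow, since even 66:44 costs only 4.2% in variance and mixed splits average 1:1. The change is worth making because the remedy is cheap and selection at entry cannot be repaired afterwards.

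**What to change.** - In 5.6, state 1:1 allocation. In 5.8, state kappa = 1.
- Delete the block-size sentence from the protocol that sites see. Say that the independent statistician alone holds the details of the list.
- Generate a within-site list compatible with 1:1. A biased-coin list (probability 2/3 to the arm that is behind) leaves nothing certain, keeps best-guess accuracy at about 62%, and has an SD of the arm difference of about 3.7.
- If tighter balance matters more, use even blocks of 4, 6 and 8 in random order: SD about 2.0 and about 2% certain, at the price of about 67% best-guess accuracy.
- Separately, and not as a remedy for predictability, stratify the comparison of new-ulcer incidence in 5.8 by site, for example with a Mantel-Haenszel risk difference, because site is the randomization stratum.

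The cost is one regenerated REDCap table and a few sentences in 5.6 and 5.8. The documents do not give recruitment status. If recruitment has begun, apply the new list to the remaining allocations only.
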